8.1 Changes in the Conduct of the Study

8.2 Changes to the Planned Analyses

- In the protocol, safety and enrolled subjects are defined as the same, all enrolled subjects who underwent the study device placement procedure, regardless of whether the study device was successfully placed or not. In this analysis plan, the safety analysis population will include all enrolled subjects who underwent a successful study device placement procedure.
- In the protocol, pre-treatment and on-treatment subjects are not specified in EP analysis population. In this analysis plan, pre-treatment subjects are excluded from EP.

9 SAS Data Transfer

All SAS reported study data will be transferred to Sebela and will be performed in compliance with CDISC (Clinical Data Interchange Standards Consortium) on issue of the final draft clinical study report (CSR). Synteract will provide metadata files along with the clinical and efficacy data.

All study data will be transferred as SAS transport files in standard SDTM/ADaM (Study Data Tabulation Model/Analysis Data Model) dataset format.

10 Reporting Conventions

The following reporting conventions will be adopted for the presentation of study data. These conventions will enhance the review process and help to standardise presentation with common notations.

10.1 General Reporting Conventions

- All tables and data listings will be developed in Landscape Orientation.
- Figures will be presented in Landscape Orientation, unless presented as part of the text in a CSR.
- Legends will be used for all figures with more than one variable or item displayed.
- Figures will be in black and white. Lines in figures should be wide enough to view the line after being photocopied.
- Specialised text styles, such as bolding, italics, borders, shading, superscripted and subscripted text will not be used in tables, figures, and data listings.
- Only standard keyboard characters should be used in tables and data listings. Special characters, such as non-printable control characters, printer specific, or font specific characters, will not be used on a table, figure, or data listing. Hexadecimal character representations are allowed.
- All titles will be centered on a page. The ICH (International Conference on Harmonisation) numbering convention is to be used for all TLFs.
- All footnotes will be left justified and displayed at the bottom of a page. Footnotes should be used sparingly and must add value to the table, figure, or data listing.
- Missing values for both numeric and character variables will be presented as "---" in a table or data listing. A zero (0) may be used if appropriate to identify when the frequency of a variable is not observed.

- All date values will be presented as YYYY-MM-DD (e.g., 2001-10-23) format. A four-digit year is preferred for all dates.
- All observed time values will be presented using a 24-hour clock HH:MM:SS format (e.g., 01:35:45 or 11:26). Seconds should only be reported if they were measured as part of the study.
- All tables, figure, and data listings will have the name of the program, location, and a date stamp on the bottom of each output.
- All analysis programs developed for a table, figure, or data listing display will be self-contained to facilitate transfer of programs to multiple computing environments and transfer to a regulatory agency (if requested).
- Listings will be sorted by subject ID number.

10.2 Population Summary Conventions

- Population(s) represented on the tables or data listings will be clearly identified in the last title of the Table as "Population: <name of population>" and will be identical in name to that identified in the protocol or SAP.
- Population sizes may be presented in the column header as (N=xxxx), where appropriate.
- Population sizes shown with summary statistics are the samples sizes (n) of subjects with non-missing values.
- All population summaries for categorical variables will include all categories that were planned and for which the subjects may have had a response. Percentages corresponding to null categories (cells) will be suppressed.
- All population summaries for continuous variables will include: N, mean, median, SD, minimum, maximum and n. Other summaries (e.g., number missing, quartiles, 95% intervals) may be used as appropriate.
- All percentages are rounded and reported to a single decimal point (xx.x). A percentage of 100% will be reported as (100). No value of 0% will be reported. Any computation of percent that results in 0% is to be presented as a blank.

10.3 Standard Calculations

Variables requiring calculation will be derived using the following formula.

- **Study Day** – Study Day 1 is defined as the date of the study device placement; the day before the study device placement is defined as Study Day -1. For a given event date, Study Day is calculated relative to the date of study device placement.

Study Day = [Event Date – Study Device Placement Date] (in days) + 1 day,
where the event date is on or after the study device placement date.

Study Day = [Event Date – Study Device Placement Date] (in days),
where the event date is before the study device placement date.

- **Age (Years)** – Age is calculated as the number of years from the date of birth to the date of informed consent using the following formula and rounded down to the nearest year.

$$\text{Age (years)} = \frac{\text{Date of informed consent} - \text{date of birth}}{365.25}$$

- **Height** – Height entries made in inches (in) are converted to centimeters using the following formula:

Height (cm) = Height (in) * 2.54, rounded to the one decimal place.

- **Weight** – Weight entries made in pounds (lbs) are converted to kilograms (kgs) using the following formula:

Weight (kg) = Weight (lb) / 2.2046, rounded to the one decimal place.

- **Body Mass Index (BMI)** – BMI is derived using following formula and rounded to one decimal place.

$$\text{BMI (kg/m}^2\text{)} = \frac{\text{weight(kg)}}{[\text{height(cm)}/100]^2}$$

BMI categorized by Underweight (< 18.5), Normal (18.5 – 24.9), Overweight (25.0 – 29.9), and Obese (\geq 30.0).

CONFIDENTIAL

11 Appendix 1: Partial Date Conventions

Imputed dates will NOT be presented in the listings.

Algorithm for Treatment Emergence of Adverse Events:

Start Date	Stop Date	Action
Known	Known/Partial/Missing	If start date < study med start date, then not TEAE; If start date ≥ study med start date, then TEAE.
Partial, but known components show that it cannot be on or after study med start date	Known/Partial/Missing	Not TEAE
Partial, could be on or after study med start date	Known	If stop date < study med start date, then not TEAE; If stop date ≥ study med start date, then TEAE.
	Partial	Impute stop date as latest possible date (i.e. last day of month if day is unknown or 31 December if day and month are unknown), then: If stop date < study med start date, then not TEAE; If stop date ≥ study med start date, then TEAE.
	Missing	Assumed TEAE
Missing	Known	If stop date < study med start date, then not TEAE; If stop date ≥ study med start date, then TEAE.
	Partial	Impute stop date as latest possible date (i.e. last day of month if day is unknown or 31 December if day and month are unknown), then: If stop date < study med start date, then not TEAE; If stop date ≥ study med start date, then TEAE.
	Missing	Assumed TEAE

CONFIDENTIAL

Algorithm for Prior/Concomitant Medications:

Start Date	Stop Date	Action
Known	Known/Partial/Missing	If start date < study med start date, then assign as prior; If start date \geq study med start date, then assign as concomitant.
Partial	Known/Partial/Missing	Impute start date as earliest possible date (i.e. first day of month if day is unknown or 1st January if day and month are unknown), then: If start date < study med start date, then assign as prior; If start date \geq study med start date, then assign as concomitant.
Missing	Known	If stop date < study med start date, then assign as prior; If stop date \geq study med start date, then assign as concomitant.
	Partial	Impute stop date as latest possible date (i.e. last day of month if day is unknown or 31 December if day and month are unknown), then: If stop date < study med start date, then assign as prior; If stop date \geq study med start date, then assign as concomitant.
	Missing	Assign as concomitant

12 Appendix 2 List of Tables, Figures, and Listings

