### 15.2 Definition of An Adverse Event

An **adverse event** is any untoward medical occurrence in a clinical investigation subject administered an investigational product and which does not necessarily have to have a causal relationship with this treatment. An AE can, therefore, be any unfavorable and unintended sign (that could include a clinically significant abnormal laboratory finding), symptom, or disease temporally associated with the use of a medicinal product, whether or not considered related to the medicinal product.

- Any medical condition or clinically significant laboratory abnormality with an onset date before the first date of attempted study device placement is usually considered to be pre-existing, and should not be documented in the eCRF as an AE, unless there is an increase in frequency or intensity of that AE, but should be recorded as medical history.
- Any AE (i.e., a new event or an exacerbation of a pre-existing condition) with an onset from the first attempt of study device placement through Study Exit should be recorded as an AE on the eCRF. All AEs must be recorded on the AE eCRF regardless of the severity or relationship to study device. It is important that Investigators also report all AEs that result in expulsion or removal of the investigational product being studied, whether serious or non-serious.

Pregnancy is an outcome, and not an adverse event in this study.

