4.2 Safety and other Variables

Safety and other measures are study device placement, safety, and tolerability.

1. Placement success

Device successfully deployed at first try rate is defined as the percentage of the number of subjects with successful deployment at first attempt among the total number of subjects with first attempt.

Device successfully deployed at second try rate is defined as the percentage of the number of subjects with successful deployment at second attempt among the total number of subjects with second attempt.

Device successfully deployed rate is defined as the percentage of the number of subjects with successful deployment in either first or second attempt among the total number of subjects enrolled.

2. Ease of placement

Five categories of how easy the device placement have been collected: Very easy, Easy, Neither Easy nor Hard, Hard and Very Hard.

Five categories of device placement pain as rated by the subject: No Pain, Some Pain, Painful, Moderately Painful and Very Painful.

Question of insertions requiring mechanical cervical dilatation has been collected.

3. Adverse events

All Adverse Events (AEs) will be coded from verbatim text to PTs and grouped by system organ class (SOC) using the Medical Dictionary for Regulatory Activities (MedDRA) (version 17.0). AEs will be collected from the beginning of the study device placement procedure through to study exit. Pre-existing conditions that worsen during a study are to be reported as AEs.

Throughout the study, all AEs will be evaluated by the investigator and noted in the AE section of the CRF.

AEs will be classified as not related, unlikely related, probably related, or related events when considering their relationship to study device, study device placement/removal procedure. Also, AEs will be classified as mild, moderate, severe when considering their severity. If the severity or relationship of an AE is missing, the severity/relationship will be coded as severe, related, respectively, i.e. worst case scenario.

Treatment-emergent AEs (TEAEs): AEs that develop or that worsen in intensity during or after the exposure to the study device.

See Appendix 1 for handling of partial dates for AEs. If it cannot be determined whether the AE is treatment emergent due to a partial onset date then it will be counted as such.

Other AE variables include study device related AEs, AEs leading to study withdrawal, AEs leading to deaths, life threatening AEs, and serious AEs (SAEs).

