6.2.9.1 Adverse Events

Number of AEs will be summarised by SOC and/or PT for the following categories of TEAEs: all AEs, SAEs, AEs related to study device, AEs related to study device placement/removal procedure, AEs leading to death, AEs leading to study device removal and AEs as primary reason for exiting study. Patients with more than one occurrence of the same SOC (PT) will be counted only once within the SOC (PT) categorisation.

AEs will also be summarised similarly by severity (i.e. mild, moderate, severe), relationship to study device (i.e. not related, unlikely related, probably related, related), relationship to placement/removal procedure (i.e. not related, unlikely related, probably related, related) and onset time frame (i.e. 0-3 months, >3-6 months, >6-12 months, >12 months). Should a subject experience more than one occurrence of the same SOC (PT), the subject's worst occurrence (worst intensity/most related causality) will be retained in the tabulation.

All AEs, including AEs that started prior to the study device placement, will be presented in data listings. In addition, separate listings of all SAEs, AEs related to study device, AEs related to study device placement/removal procedure, AEs leading to death, AEs leading to study device removal and AEs as primary reason for exiting study will be provided. In case of any AEs reported from study device insertion failure subjects, selected AE tables will be repeated for all enrolled subjects for all AEs.

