Listing 16.2.7.1 Adverse Events (All Enrolled Subjects) Part 1 of 2

Subject ID	Any AE	AE #	System Organ Class // Preferred Term // Verbatim Text	Start Date(Study Day)/ End Date (Study Day)/ Duration/ TEAE	Severity	Worsening of Pre-existing Condition	Related to Bleeding	Relationship to Study Device	Relationship to Placement/ Removal Procedure	Action Taken with Study Device	Treatment of Event	Outcome
xxx-xxx	No											
xxx-xxx	Yes	1	xxxxx// xxxxx// xxxxx	YYYY-MM-DD (xx)/ YYYY-MM-DD (xx)/ xx/ No	Mild	No	No	Not Related	Not Related	None	Medication	Recovered
		2	xxxxx// xxxxx// xxxxx	YYYY-MM-DD (xx)/ YYYY-MM-DD (xx)/ xx/ Yes	Moderate	Yes	Yes	Unlikely Related	Unlikely Related	Removed	Non-Drug Treatment	Resolved with Sequelae
		3	xxxxx// xxxxx// xxxxx	YYYY-MM-DD (xx)/ YYYY-MM-DD (xx)/ xx/ Yes	Life Threatening	No	No	Probably Related	Probably Related	Expelled	Hospitalization	Ongoing
		4	xxxxx// xxxxx// xxxxx	YYYY-MM-DD (xx)/ YYYY-MM-DD (xx)/ xx/ Yes	Fatal	Yes	Yes	Related	Related	Not Applicable	None	Fatal
xxx-xxx	Yes	1	xxxxx// xxxxx// xxxxx	YYYY-MM-DD (xx)/ YYYY-MM-DD (xx)/ xx/ Yes	Moderate	No	No	Not Applicable	Not Applicable	Expelled	Hospitalization	Unknown

[1] Did the AE require inpatient hospitalization or prolong an existing hospitalization?

[2] Did the AE result in persistent or significant incapacity or substantial disruption of the ability to conduct normal life functions?

[3] Did the AE result in a congenital anomaly or birth defect?

Note: An AE that started on or after the date/time of study device placement, or an AE with an unknown/not reported onset date/time is defined as a TEAE.

Note: AEs are coded using MedDRA v xxx.

Note: Study day is relative to the date of study device successfully deployed. Duration in days is calculated as end date –start date +1.

AE = Adverse Event; MedDRA = Medical Dictionary for Drug Activities; TEAE = Treatment-Emergent Adverse Event.

Program Location: \\x\xxx\xxx\xxx\xxxxxx\xxxxxxxxxxxxxx\xxx\xxxx.sas

date

time

Programmer notes: Sort by AE # within each subject.

CONFIDENTIAL

Sebela Pharmaceuticals Development LLC
CMDOC-0022

Page x of y

Listing 16.2.7.1
Adverse Events (All Enrolled Subjects)
Part 2 of 2

Subject ID	Any AE	AE #	Serious	Result in Death	Date of Death/ Death Certificate/ Autopsy	Life-threatening	Hospitalization[1]/ Date of Admission/ Date of Discharge	Life functions[2]	Birth Defect[3]	Important Medical Event	Intervention
xxx-xxx	No										
xxx-xxx	Yes	1	No	No		No		No		No	No

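### SAP 4.2 counts adverse events that worsen on the device as treatment-emergent, but Appendix 1 has no worsening branch, so a worsened condition entered with its original onset date is left out of the TEAE tables

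*SAP*

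**What the plan says.** SAP 4.2, under adverse events, defines TEAEs as "AEs that develop or that worsen in intensity during or after the exposure to the study device". It adds: "Pre-existing conditions that worsen during a study are to be reported as AEs." For dates it refers onward: "See Appendix 1 for handling of partial dates for AEs."

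The treatment-emergence table in SAP Appendix 1 covers more than partial dates. Its first row deals with known start dates: "If start date < study med start date, then not TEAE", whatever the stop date. Its second row covers start dates described as "Partial, but known components show that it cannot be on or after study med start date", and these are also not TEAE. The remaining rows, for an ambiguous partial or a missing start date, decide on the stop date and assume TEAE if that is missing too.

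The footnotes of Tables 14.3.1.3.1, 14.3.1.8, 14.3.1.9 and 14.3.1.11 to 14.3.1.13 define a TEAE by onset at or after placement, or by an unknown onset. They do not mention worsening.

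Under protocol 15.2, first bullet, a condition with onset before the first placement attempt is medical history and not an AE, "unless there is an increase in frequency or intensity of that AE". The second bullet speaks of an exacerbation of an existing condition as an AE with its own onset from the first attempt onward. SAP Listing 16.2.7.1 has a Yes/No column "Worsening of Pre-existing Condition". SAP 6.2.9.1 says: "All AEs, including AEs that started prior to the study device placement, will be presented in data listings."

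**The concern.** The SAP has a definition with two limbs, new and worsened, and an algorithm that implements only the first. Programmers will code the algorithm and print the footnotes, so the worsening limb may never take effect, although a field identifying worsening is collected.

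The classification of one clinical event would then depend on how a site dates it. Relative to 4.2 the error runs one way, towards lower TEAE rates. The protocol's list of events for special attention (20.7) includes acne, depression, dysmenorrhea and headache or migraine. Women may have any of these before placement, so worsening is a realistic way for them to occur in this trial.

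**Working it through.** The plan gives no figure for this point, so the check is one of logic: apply each stated rule to the same events and compare.

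Inputs: the SAP 4.2 definition, the Appendix 1 rows, and the footnote of Table 14.3.1.3.1. Appendix 1 refers to a study medication start date; I read this as the placement date. Illustrative dates: placement 15 March 2017, original onset 5 January 2016, worsening 13 May 2017 (Day 60).

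| Event as recorded | SAP 4.2 | Appendix 1 | Footnote |
|---|---|---|---|
| New onset after placement | TEAE | TEAE | TEAE |
| Pre-existing, did not worsen | not TEAE | not TEAE | not TEAE |
| Worsened Day 60, original onset date entered | **TEAE** | **not TEAE** | **not TEAE** |
| Worsened Day 60, only the year 2016 entered as start | **TEAE** | **not TEAE** | **not TEAE** |
| Worsened Day 60, worsening date entered as start | TEAE | TEAE | TEAE |
| Worsened, start given only as 2017, stop after placement | TEAE | TEAE (on stop date) | no rule for partial dates |
| Worsened, start missing, stop after placement | TEAE | TEAE (on stop date) | TEAE |

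The rules disagree in two patterns: a known earlier start, and a partial start that must be earlier. In both the event worsened on the device. Entering the worsening date as the start removes the disagreement.

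Next, which outputs lose the event. The Safety-population TEAE tables would omit it, including severity (14.3.1.8), relatedness (14.3.1.9, 14.3.1.10), device removal (14.3.1.5), study exit (14.3.1.6) and onset time frame (14.3.1.12, 14.3.1.13). Four tables in the same block are All Enrolled and not titled treatment-emergent: 14.3.1.1.2, 14.3.1.2.2, 14.3.1.3.2 and 14.3.1.4.2. The event would appear in those. SAP 6.2.9.1 makes these repeats selective and conditional on AEs in women whose insertion failed, whereas the table index lists them without a condition. No All Enrolled summary table is indexed for severity or relatedness by preferred term, for removal or for onset time; removal and exit have All Enrolled listings, which give no rates.

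On size, the documents do not say how many events are dated either way. The effect per woman is simple arithmetic: if all 250 planned women have the device placed, one woman lost from a preferred term lowers its TEAE rate by 1/250 = 0.4 percentage points. For an assumed one to five women per term the range is 0.4 to 5/250 = 2.0 points.

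**The case against.** The strongest reply is that the second bullet of protocol 15.2 already settles the matter. The exacerbation is the AE, its onset falls after the attempt, and the underlying condition goes to medical history, which has its own onset date. SAP 4.2 likewise collects AEs from the start of the placement procedure. On that reading the recorded start is the worsening date and Appendix 1 returns TEAE. In the sample rows of Listing 16.2.7.1, both events flagged as worsened are marked TEAE, though mock rows are weak evidence. This reply stands in part: it shows that events need not be lost. It does not close the gap, because neither document tells sites which start date to enter, and 6.2.9.1 expects AEs that start before placement.

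A second reply is that Appendix 1 concerns partial dates and the definition stays in 4.2. But its first row classifies known dates, and the table footnotes repeat the onset-only rule.

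A third is that dysmenorrhea is captured separately, in the e-diary tables of menstrual pain by cycle (14.3.6.3.1 to 14.3.6.3.4). That is true, and it reduces the stake for that term. It does not help for headache, acne or depression.

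Some stronger readings are tempting but not supported:

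- A reader might infer that AE records starting before placement are mainly worsened conditions. They need not be. Day 1 is the date of successful deployment (SAP 1.2) and a second attempt may follow within a week of a failed first (protocol 12.2), so an AE between attempts also starts before placement.
- A reader might infer that every TEAE decision rests on the start date. Ambiguous partial and missing starts are decided on the stop date.
- A reader might infer that the whole table block from 14.3.1.1.1 to 14.3.1.13 is affected. The four All Enrolled tables are not.
- A reader might put a percentage on the understatement. That needs a share of misdated events and a true event rate, and the documents give neither.

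**Conclusion.** The inconsistency is real. SAP 4.2 makes on-device worsening treatment-emergent; two rows of Appendix 1 and the TEAE footnotes say otherwise when the recorded start precedes placement. The consequence is conditional: an event is lost from the TEAE tables only where the original onset date, or a partial date that must be earlier, is entered. It remains in the listings and, where produced, in the All Enrolled AE and SAE tables.

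The documents do not support a claim that worsened conditions are dropped in general, or any estimate of how many are. The 0.4 points per woman assumes 250 successful placements and that she has no other TEAE record under the same term; with fewer placements it is slightly larger. Because the remedy is small, it is worth making before the tables are run.

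**What to change.** Add a row at the top of the Appendix 1 algorithm: an AE with the worsening flag set to Yes, with worsening on or after placement and no known stop date before placement, is a TEAE even if its recorded start is earlier. Bring the TEAE table footnotes into line with SAP 4.2.

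Listing 16.2.7.1 shows the flag without a date of worsening, so the SAP should say how the timing is established. AE collection begins with the placement procedure, so the main case to separate is worsening between a failed first attempt and a successful second.

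State also that the worsening date serves as the AE start date in the onset-time-frame tables. Otherwise an event with an earlier start has no place there, since the intervals begin at Day 1 or at 0 to 3 months. Where no worsening date is available, show the event in the existing Missing row of Table 14.3.1.1.1 and only in the overall column of Tables 14.3.1.12 and 14.3.1.13.

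A site instruction to enter the worsening date as the AE start would also remove the ambiguity, but records already entered with the original onset would still need a query or the new row.

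The cost is one algorithm row, a footnote change and a date rule, using an item already collected. TEAE rates may come out slightly higher.
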